State of the question Purpose of the research	
The incidence of cancer in elderly subjects is constantly increasing and improving their management by taking into account their specific needs is one of the objectives of the 3rd cancer plan published in February 2014. New anti-cancer molecules are placed on the market after validation by clinical trials in which elderly subjects are under-represented. There is therefore little data available on the toxicity of these new molecules in elderly patients. Tyrosine kinase inhibitors (TKIs) are indicated in different types of metastatic cancer. Several elements suggest that their toxicity is higher in elderly subjects than in younger subjects: firstly, the pharmacokinetic modifications, drug interactions and more fragile ground, making these toxicities more severe. As the geriatric population is heterogeneous, identifying those subjects most at risk of complications is a crucial issue. It is also a major socio-economic issue, the occurrence of adverse events being the source of a significant additional cost. Our study will evaluate prospectively (cohort) among geriatric (G8 screening score, ADL, IADL, MNA, comorbidities, Performance Status, Get up and Go Test, visual or verbal fatigue scale), biological, pharmacokinetic and pharmacogenomic data, those prognostic factors of severe TKI toxicity in the elderly. The primary objective of this study is to predict severe toxicity (defined as the occurrence of treatment-related adverse events resulting in either discontinuation of more than 3 weeks of treatment, permanent discontinuation of treatment, hospitalisation, or death, i.e. disability or significant or lasting incapacity) of TKIs prescribed in the context of the Marketing Authorisation (MA) in subjects over 70 years of age. The secondary objectives are the rate of non-progression at 6 months (percentage of patients with complete response, partial response or stable disease according to RECIST v1.1 criteria), progression-free survival and the correlation between the pharmacogenomic data and the rate of non-progression at 6 months.

Target population	This study concerns patients aged 70 and over with cancer and treated with a TKI prescribed in the context of the Marketing Authorisation and having signed an informed consent.

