Collection of blood samples	As part of this protocol, two blood samples ($2 * 5 \text{ ml} = 10 \text{ ml}$) will be taken for each patient. An initial sample will be taken before the start of treatment upon inclusion and a second sample will be taken at the end of the first month of treatment. Each sample will be anonymised and the following information will appear on the tubes: name of the study, number of the study centre, number of the patient in this centre, date of sample and type of analysis carried out (pharmacokinetics and pharmacogenomics). At the end of the study, blood samples intended for pharmacokinetic analyses will be sent to the pharmacology department of the Bordeaux University Hospital headed by [name], while the samples intended for pharmacogenomic analyses will be sent quarterly (according to the rhythm of inclusions) to the biological resources centre of Institut Bergonié. These samples will be accompanied by the sample routing form on which the date of signing of the sample preservation consent will be indicated. These biological samples will never be linked to nominative data and will be used for research purposes only. Any samples not immediately used will remain stored for future use to help researchers advance their knowledge of oncology and pharmacology.
Study duration	Enrolment period: 24 months Follow-up: 12 months Total duration: 36 months
Information collection methods	After checking the eligibility criteria, and once the informed consent has been signed, eligible patients will be registered centrally at Institut Bergonié by the study coordinator CRA (request by fax from each participating centre). A confirmation of inclusion with an inclusion number will be returned to the investigator. The patient's enrolment in the study will not be effective until the inclusion number has been assigned.

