Data analysis method	
Primary endpoints: prediction of severe toxicity (defined as the occurrence of adverse events attributable to treatment resulting in either discontinuation of more than three weeks of treatment, permanent discontinuation of treatment, hospitalisation, death, disability or significant or lasting incapacity) of TKIs prescribed in the context of the Marketing Authorisation in patients aged 70 years or over with cancer.
 
Secondary endpoints: description of toxicities, non-progression rate at 6 months and progression-free survival at one year.
 
Analysis of toxicity: The severe toxicity rate, along with the incidence rates for toxicities grades 1-4 will be reported according to the eligible and evaluable population. These endpoints will be described using frequency, percentage and 95% confidence interval. The toxicity rate will also be reported by subgroup of patients according to the TKI. Prognostic factors of severe toxicity will be evaluated using logistic regression analyses.
 
Non-progression analysis: The non-progression rate at 6 months will be reported according to the eligible and evaluable population, but also by subgroup of patients according to the TKI used. This endpoint will be described using frequency, percentage and 95% confidence interval. Prognostic factors (clinical and geriatric) of 6-month non-progression rates will be evaluated using logistic regression analyses.
 
Analysis of PFS: PFS will be analysed using the Kaplan-Meier method. Median survival will be presented with a 95% confidence interval. Median follow-up will be calculated using the reverse Kaplan-Meier method. Multivariate analyses will be performed according to the Cox proportional hazards model after verifying the risk proportionality assumption.
 
Intermediate statistical analysis: After the inclusion of the first 150 patients, an intermediate statistical analysis will be performed.

Institut Bergonié
Pre-ToxE Protocol

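### Prediction of severe toxicity is primary, but the synopsis plans only logistic regression of prognostic factors, with no measure of predictive performance and no separate handling of month-1 drug levels

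*Combined protocol and SAP*

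**What the plan says.** The synopsis paragraph on the purpose of the research states: "The primary objective of this study is to predict severe toxicity". The Data analysis method section repeats this at endpoint level: "Primary endpoints: prediction of severe toxicity". The motivation is individual risk: "identifying those subjects most at risk of complications is a crucial issue".

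The same purpose paragraph also describes the work as evaluating "those prognostic factors of severe TKI toxicity in the elderly". The candidates are geriatric ("G8 screening score, ADL, IADL, MNA, comorbidities, Performance Status, Get up and Go Test, visual or verbal fatigue scale"), biological, pharmacokinetic and pharmacogenomic.

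Under Analysis of toxicity, the plan is to report rates with 95% confidence intervals, overall and by TKI, and then one modelling sentence: "Prognostic factors of severe toxicity will be evaluated using logistic regression analyses".

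Severe toxicity means attributable adverse events leading to any of: "discontinuation of more than three weeks of treatment, permanent discontinuation of treatment, hospitalisation, death, disability or significant or lasting incapacity". For pharmacokinetics, "a second sample will be taken at the end of the first month of treatment"; the flowchart places it at D28, ±2 days.

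**The concern.** Finding factors associated with an outcome and showing that the outcome can be predicted are different tasks. Odds ratios serve the first. The second needs a statement of how well the model separates patients who will have severe toxicity from those who will not, whether its predicted risks are about right, and how far both would hold in new patients. The synopsis mentions none of these, so its primary question could be left unanswered. It could also be answered with a figure taken from the same patients who built the model, which would look better than it should.

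The second issue is time order. A baseline score precedes the outcome. A drug level at about day 28 may not: if treatment was interrupted for toxicity before the sample, the level is partly a result of the toxicity. Used as an ordinary candidate, it could mask or reverse a true link between exposure and toxicity.

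**Working it through.** **1. The plan's own figure.** Inputs from Number of subjects: rate 30%, n = 250. Wald interval: 0.30 ± 1.96 × √(0.30 × 0.70 / 250) = 0.30 ± 0.057, or 24.3% to 35.7%. This matches the stated interval. The sample size therefore rests on the precision of a rate, not on a prediction model. Expected events: 0.30 × 250 = 75.

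**2. Aim against analysis.**

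| Needed to show prediction | Found in the synopsis or flowchart |
|---|---|
| Discrimination (c-statistic, sensitivity, specificity) | None |
| Calibration | None |
| Internal validation (bootstrap, cross-validation, split sample) | None |
| Association with candidate factors | Logistic regression |
| Frequency of severe toxicity | Rate with 95% interval |

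The intermediate analysis after 150 patients is not described as a model-building or validation step.

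**3. How favourable would an uncorrected c-statistic be?** Simulation, 300 datasets, n = 250, 30% events, unpenalised logistic regression, all nine geriatric items of flowchart footnote 3 entered (75 / 9 = 8.3 events per item). The signals are assumptions; the documents give none.

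| Assumed truth | Same patients | New patients | Excess | Calibration slope |
|---|---|---|---|---|
| Four true factors, OR 1.42 per SD, independent | 0.715 | 0.656 | 0.059 | 0.69 |
| Four true factors, pairwise correlation 0.3 | 0.761 | 0.716 | 0.045 | 0.78 |
| No true factor | 0.614 | 0.500 | 0.114 | – |

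Repeat runs agree to about 0.01. In the last row, nine useless items would look mildly predictive.

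**4. Does internal validation correct this?** In the same nine-item setting, the 10-fold cross-validated c-statistic was within 0.005 of the new-patient value. A ridge penalty changes the new-patient c-statistic by at most about 0.01 (12-term simulations). Validation does the work, not the penalty.

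**5. Timing of the pharmacokinetic sample.** An interruption must exceed three weeks (21 days) to count. To have passed that limit by day 28, it must have begun by about day 28 − 21 = 7. One that begins after about day 7 and is still running at the sample is not yet severe toxicity, although the level may already be lower.

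Simulation, 400,000 patients, assumed true OR 1.5 per SD. Assumed: 20% or 40% of events begin before the sample, and all of these patients are sampled with a level lowered by 1 or 2 SD.

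| Analysis | 20% early (1 SD; 2 SD) | 40% early (1 SD; 2 SD) |
|---|---|---|
| Timing ignored | 1.20; 0.99 | 0.99; 0.72 |
| Only patients already meeting the definition excluded; a quarter to a half of early events are running interruptions | range 1.41 to 1.17 | range 1.28 to 0.91 |

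If every affected patient is excluded, the OR is 1.49. With a true OR of 1.0, ignoring timing gives 0.55 to 0.83.

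**The case against.** The purpose paragraph also speaks of prognostic factors, and logistic regression suits that aim. If association is all the sponsor wants, changing the wording of the objective and endpoint removes the prediction problem without any new analysis. This stands, and the fix treats it as an equal route. It does not rescue the text as it is, because objective and endpoint both say prediction.

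The plan states no c-statistic, so the excess in the working belongs to a step the plan does not describe, and it depends on how many items are entered. This also stands. The figures show why an uncorrected c-statistic would not fill the gap; they are not an error in a planned result.

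The pharmacokinetic bias may be smaller than the timing-ignored row suggests. Patients who die before day 28 have no sample, those who stop permanently may have none, and hospitalisation need not lower a level. If half to three quarters of early events have no sample (assumed), ignoring timing gives 1.17 to 1.41 with 20% early events and 0.92 to 1.29 with 40%. The time-order problem remains; its size is open.

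Finally, only a synopsis and flowchart were available. A fuller analysis section could already contain these methods.

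**Conclusion.** The mismatch holds in the supplied text: prediction is primary, and the planned analysis gives rates and odds ratios but no measure of prediction. This does not depend on any simulation. The illustrative excess of an uncorrected c-statistic, about 0.04 to 0.06 with signal and about 0.11 with none, rests on nine items entered and on assumed effects. The pharmacokinetic timing problem is also real, but its size rests on early-event shares, level shifts and sampling rates that the documents do not give.

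A reader might infer more than this, without support:
- That the study will report an inflated c-statistic. None is planned.
- That logistic regression is the wrong method or must be penalised. Plain logistic regression with internal validation closes the gap.
- That odds ratios should be demoted. Prognostic factors are a stated aim.
- That the exposure–toxicity link will be reversed. This happens under only some of the assumed settings.

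This is a cheap improvement: high confidence in the mismatch, less in the size of the pharmacokinetic effect.

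**What to change.** Take either of two equal routes.

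**(a) If prediction is meant**, keep the logistic regression sentence under Analysis of toxicity and add: *Prediction will be assessed for one multivariable logistic model using baseline candidates fixed in writing before any outcome analysis. The c-statistic will be estimated by internal validation of the whole modelling process (10-fold cross-validation stratified by outcome and repeated, computed within held-out folds and averaged) and reported with an approximate 95% interval; the calibration slope is supportive. The uncorrected c-statistic will not be reported as the result.* Penalisation is optional, and odds ratios remain a reported aim.

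**(b) If only association is meant**, reword the primary objective and the primary endpoint as identifying factors associated with severe toxicity, and make no claim of prediction.

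**Under either route**, add: *Month-1 pharmacokinetic values are not combined with baseline predictors. Their association with later severe toxicity is analysed separately in patients who, at the sample, have had no severe toxicity and no treatment interruption for an adverse event that later counts as severe toxicity. Events are dated by the onset of the adverse event or interruption, not by when the three-week limit is passed.* Levels lowered by an interruption that stays short are not removed by this rule; state that as a limit.

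**Cost.** SAP wording and some programming. The reported c-statistic will be less favourable and imprecise: its SD was about 0.04 to 0.05 in simulations of a penalised model with 12 terms (nine items plus three assumed TKI terms; 75 / 12 = 6.25 events per term). The pharmacokinetic analysis loses events: 75 × 0.8 = 60 or 75 × 0.6 = 45 remain if 20% or 40% begin before the sample (assumed). No extra patients or data are needed, provided onset dates are recorded with the toxicity data already collected.

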Number of subjects	In this study, we predict that approximately 30% of patients will experience severe toxicity. A population of 250 eligible and evaluable patients will allow us to estimate this proportion with an accuracy of $\pm 5\%$, leading to a 95% confidence interval (24.3%; 35.7%). Subgroup analyses will also be carried out. Subgroups of patients will therefore be defined according to the TKI treatment received (pazopanib, regorafenib, sorafenib, etc.). Assuming that 50 patients are included in a subgroup with a toxicity rate of 30%, the resulting precision will be $\pm 12\%$, for a 95% confidence interval (17.3% ; 42, 7%).
---------------------------	--

STUDY FLOWCHART

		TREATMENT					Follow-up (Beyond 28 days after TKI discontinuation and up to 12 months after TKI initiation)
	SCREENING	Start of treatment D1	Month 1 (D28, ±2 days)	Month 2 (D56, ±2 days)	Month N	Discontinua tion of treatment (within 28 days)	
TKI	Information		MA				
Consultation	X	X	X				X
Eligibility criteria	X						
Informed consent	X						
Demographic data	X						
Height	X						
Weight	X			X			
History of the disease / Medical history / Previous treatments	X						
Performance status (ECOG)	X	X	X				
Biological assessment	X ¹						
Tumour evaluation	X ²		According to the centre's routine practice				
Geriatric evaluation	X ³			X ⁴		X ⁴	
Blood sample for pharmacogenomics		X					
Blood sample for pharmacokinetics			X				
Toxicities			X			X ⁵	
Concomitant treatments			X			X ⁵	
Vital status							X ⁶

1 Within 7 days before D1 of treatment initiation (same day possible): Haematology (CBC, platelets), Biochemistry (sodium, potassium, calcium, magnesium, phosphorus, glucose, LDH, urea, creatinine, ASAT, ALAT, Alkaline Ph., total bilirubin, albumin, total protein), Coagulation (INR, PT, aPTT), Thyroid function (free T4, TSH).

2 Within 4 weeks before D1 of treatment initiation (same day possible).

3 Within 7 days before D1 of treatment initiation (same day possible): G8, Charlson, Cardiovascular diseases, ADL, IADL, ECOG, Get Up and Go Test, verbal or visual fatigue scale, MNA.

4 Evaluation method during a consultation or telephone interview: % weight loss over the past few months, falls, verbal fatigue scale, ADL, IADL.

5 To be collected for 28 days after discontinuation of treatment.

6 Follow-up according to the centre's routine practice.

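### The 6-month non-progression rate is reported in an undefined evaluable population, so patients who die before a scan can leave the denominator and raise the rate

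*Combined protocol and SAP*

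**What the plan says.** All references are to the combined protocol and SAP.

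- **State of the question / Purpose of the research** defines the 6-month rate as the "percentage of patients with complete response, partial response or stable disease according to RECIST v1.1 criteria". The same variable is to be correlated with the pharmacogenomic data.
- **Data analysis method, non-progression analysis**: "The non-progression rate at 6 months will be reported according to the eligible and evaluable population". The same rate is broken down by TKI and given as a count and percentage with its 95% CI. The outcome is also modelled: "Prognostic factors (clinical and geriatric) of 6-month non-progression rates will be evaluated using logistic regression analyses".
- **Study flowchart**: after baseline, the tumour evaluation row reads "According to the centre's routine practice". Vital status is marked for the follow-up column, which runs to 12 months after TKI initiation.
- **Data analysis method, PFS**: Kaplan-Meier and Cox analyses are planned. The PFS event is not defined.

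The text does not say who is evaluable. It also does not say how a patient is classified who dies, stops treatment or has no scan before month 6.

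**The concern.** RECIST response categories do not describe a patient who has died. With no scan fixed at or near 6 months, a patient who dies before a post-baseline scan has no RECIST status. For a response-based endpoint, *evaluable* usually means having such a status, so this patient would be left out instead of being counted as a failure.

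The plan itself makes such patients foreseeable. Its severe toxicity definition includes "permanent discontinuation of treatment, hospitalisation, death, disability or significant or lasting incapacity", and under Number of subjects "we predict that approximately 30% of patients will experience severe toxicity". Not all of these patients would miss a scan, and the plan gives no early-death rate. Still, those lost would tend to be the patients the study exists to characterise.

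Three results use the variable: the crude rate (overall and by TKI), the logistic model of clinical and geriatric factors, and the pharmacogenomic correlation. If PFS counts death as an event, as is usual, the same patient would be a failure in one secondary result and absent from the other. An undefined term also leaves the choice open until data have been seen, including at the analysis after 150 inclusions.

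**Working it through.** **Inputs.** N = 250 overall ("A population of 250 eligible and evaluable patients will allow us to estimate this proportion") and 50 in an assumed TKI subgroup, both from Number of subjects. The plan gives neither an expected non-progression rate nor the number who will die or go unassessed before month 6. Both are assumptions below, shown over a range.

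**1. The plan's own figures.** The only precision stated is for the 30% severe toxicity rate. The Wald half-width is 1.96 × √(p(1 − p)/n).
- n = 250: 1.96 × √(0.3 × 0.7/250) = 5.68 points, giving 24.3% to 35.7%.
- n = 50: 1.96 × √(0.3 × 0.7/50) = 12.70 points, giving 17.3% to 42.7%.

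Both stated intervals reproduce. No figure is stated for non-progression, and the point does not depend on these.

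**2. Dropping failures.** With k non-progressors among N patients and m failures dropped, the rate moves from k/N to k/(N − m), a factor of N/(N − m). For N = 250 the factor is 250/225 = 1.11 at 10% dropped and 250/200 = 1.25 at 20%.

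| Assumed true rate | 10% dropped | 20% dropped |
|---|---|---|
| 30% (75/250) | 75/225 = 33.3% | 75/200 = 37.5% |
| 40% (100/250) | 100/225 = 44.4% | 100/200 = 50.0% |
| 50% (125/250) | 125/225 = 55.6% | 125/200 = 62.5% |
| 60% (150/250) | 150/225 = 66.7% | 150/200 = 75.0% |

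The same percentages hold in a subgroup of 50, for example 20/50 = 40.0%, 20/45 = 44.4% and 20/40 = 50.0%.

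**3. Patients alive without a scan.** Step 2 treats every dropped patient as a failure, which is certain only for deaths. Take 50 patients: 22 in CR, PR or SD, 5 early deaths, and 5 alive but unassessed.
- All 10 counted as failures: 22/50 = 44.0%.
- Deaths as failures, the 5 alive as non-progressors: 27/50 = 54.0%.
- All 10 dropped: 22/40 = 55.0%.

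Dropping all 10 overstates the rate by between 55.0 − 54.0 = 1.0 point and 55.0 − 44.0 = 11.0 points. The larger figure is the upper bound.

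**4. Comparison between TKIs.** Equal rates with equal proportional loss are inflated by the same factor. The order can change when loss differs. Suppose TKI A has 24/50 = 48.0% with no early loss, and TKI B has 22/50 = 44.0% with all patients counted. If 8 early deaths on B are dropped, B becomes 22/42 = 52.4%.

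**5. Logistic model.** Assume 50/100 fit and 30/100 frail non-progressors: OR = (50/50)/(30/70) = 2.33. Dropping 20 frail failures only gives (50/50)/(30/50) = 1.67. Dropping 20 failures from each group gives (50/30)/(30/50) = 2.78. The direction depends on which group loses the larger share of its failures.

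**The case against.** The strongest reply is that exclusion is inferred. Read literally, the definition is a percentage of patients, and a patient who has died is in none of the three RECIST categories, so would count as a failure. The analysis plan uses the same population phrase for toxicity, where death is part of the endpoint, and the sample size section puts that population at 250, the number to be included. If it is one population, early deaths are in it. The text also reads as a synopsis, and a fuller version might hold the definition. All this stands as a possible reading. It does not settle the matter, because the term is undefined and the opposite reading is the usual one for a RECIST endpoint.

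A second reply is that PFS already covers this, that toxic deaths count in the primary endpoint (also reported by TKI), and that the endpoint is secondary with no formal comparison of TKIs. That limits the importance. It does not repair the by-TKI rates, the logistic model or the pharmacogenomic correlation.

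A third reply concerns size. In a subgroup of 50 at 40%, the 95% interval is 26.4% to 53.6%, a half-width of 13.6 points, wider than the shift of 4 to 10 points. That is correct, but the shift is systematic and does not shrink with more patients.

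A reader might infer three stronger things. None is supported.
- *The plan excludes early deaths.* It does not say so.
- *A TKI with toxic early deaths will look better than the others.* That needs early loss to differ between TKIs, and the plan gives no early-loss rates.
- *Frailty effects will be weakened.* Step 5 shows that this depends on frail patients losing the larger share of their failures.

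**Conclusion.** The point holds as a gap in the estimand of a secondary endpoint. As written, the plan allows patients who die before a scan to leave the denominator and the logistic model. Each death so dropped raises the rate. At an assumed true rate of 40%, the increase is at most 44.4 − 40.0 = 4.4 points with 10% dropped and 50.0 − 40.0 = 10.0 points with 20% dropped. The base rate and both loss fractions are assumptions. The upward direction is certain for deaths. For patients alive without a scan, the truth lies in a best-case to worst-case range. The primary severe toxicity endpoint is not affected.

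**What to change.** - **Population and endpoint.** Report the rate, overall and by TKI, in all eligible patients who started the TKI. Define non-progression as alive without progression 6 months after initiation, with death from any cause before 6 months as failure.
- **Estimate.** Use the 6-month Kaplan-Meier PFS estimate with its 95% CI, and state that the PFS event is progression or death.
- **Logistic model.** Count deaths before 6 months as failures. A patient alive without an assessment has no binary outcome, so give best-case and worst-case results for that group.
- **Transparency.** State the analysis window around month 6 that makes a patient assessed, report the number unassessed per TKI, and keep the RECIST-evaluable percentage as supportive.

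The best-case and worst-case results are also needed because Kaplan-Meier assumes uninformative censoring. If patients stop being scanned because they are declining, the 6-month estimate is itself too high.

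**Cost.** The change is in SAP wording and uses the planned PFS analysis and vital status. It does not rely on clinical progression without a scan, which the flowchart does not list as collected. The price is a somewhat lower reported rate and a little more analysis.

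### The 250 patients are justified only for estimating a 30% toxicity rate; nothing shows that about 75 events suffice for the primary prediction objective, and no candidate limit, penalisation or validation is stated

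*Combined protocol and SAP*

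**What the plan says.** The Combined protocol and SAP, under 'Purpose of the research', states: "The primary objective of this study is to predict severe toxicity". The 'Data analysis method' section repeats this as the primary endpoint: "Primary endpoints: prediction of severe toxicity". The factors are to be sought in four domains: geriatric, biological, pharmacokinetic and pharmacogenomic.

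The analysis given for this objective, under 'Analysis of toxicity', is one sentence: "Prognostic factors of severe toxicity will be evaluated using logistic regression analyses". It gives no candidate list or maximum, selection rule, position on penalisation, internal validation, performance target or multiplicity control.

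'Number of subjects' starts from an expected rate ("we predict that approximately 30% of patients will experience severe toxicity") and derives 250 from the 95% confidence interval around it: "A population of 250 eligible and evaluable patients will allow us to estimate this proportion". The only other calculation is the precision of the same rate in a 50-patient TKI subgroup. Neither refers to prediction.

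The study flowchart footnotes list what is measured before treatment. Footnote 3 has nine geriatric items. Footnote 1 has haematology, coagulation and thyroid tests and a biochemistry panel ("sodium, potassium, calcium, magnesium, phosphorus, glucose, LDH, urea, creatinine, ASAT, ALAT, Alkaline Ph., total bilirubin, albumin, total protein").

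**The concern.** A sample that estimates a proportion adequately can be far too small to develop a prediction model. The model's requirement depends on the number of events, the number of parameters considered and how strongly they predict. The plan addresses none of these for its primary objective.

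With many candidates and few events, maximum-likelihood coefficients are too large, the factors that look important are partly chosen by chance, and the apparent c statistic hides both problems. Candidates dropped after a univariable test on the same data still contribute to the overfitting. The study's stated aim is to identify the older patients most at risk. An unstable factor list, or risks that are too extreme, would fail that aim while looking successful in the study's own data.

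**Working it through.** **1. The plan's own figures.** With p = 0.30, the half-width is 1.96 × √(p(1 − p)/n).
- n = 250: 5.68 points, so 24.3% to 35.7%, as stated.
- n = 50: 12.7 points, so 17.3% to 42.7%, as stated.

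The intervals reproduce. The accompanying ±5% is loose: the half-width is 5.7 points, and a true ±5% would need 0.21 × (1.96/0.05)² ≈ 323 patients.

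**2. Events.** 0.30 × 250 = 75.

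**3. Measurements available as candidates.**
- Geriatric (footnote 3): 9.
- Biological (footnote 1): 2 haematology (CBC counted once) + 15 biochemistry + 3 coagulation + 2 thyroid = 22.
- Pharmacokinetic and pharmacogenomic: number not stated; at least 1 each is assumed, so 2.

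The total is 9 + 22 + 2 = 33, and 75/33 = 2.3 events per measurement. Over the plan's own interval for the rate this runs from 0.243 × 250/33 = 1.8 to 0.357 × 250/33 = 2.7.

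**4. Expected shrinkage.** The relation used is P = n(S − 1) ln(1 − R²/S), where P is the number of parameters, S the expected shrinkage factor (target 0.9) and R² the Cox-Snell value. At 30% events the maximum Cox-Snell R² is 1 − exp{2[0.3 ln 0.3 + 0.7 ln 0.7]} = 0.705. The documents give no R², so Nagelkerke values of 0.10 to 0.30 are assumed. For Nagelkerke 0.20, R² = 0.20 × 0.705 = 0.141, and P = 250 × (−0.1) × ln(1 − 0.141/0.9) = 4.3.

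| Nagelkerke R² (assumed) | Parameters supported by n = 250 at S = 0.9 | S with 7 | S with 9 | S with 33 | n needed for 33 at S = 0.9 |
|---|---|---|---|---|---|
| 0.10 | 2.0 | 0.73 | 0.67 | 0.37 | about 4,040 |
| 0.15 | 3.1 | 0.80 | 0.76 | 0.48 | 2,639 |
| 0.20 | 4.3 | 0.85 | 0.81 | 0.55 | 1,936 |
| 0.30 | 6.7 | 0.90 | 0.87 | 0.66 | 1,232 |

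**5. Simulation.** Settings: n = 250, 30% events, 33 predictors with pairwise correlation 0.2, 5 of them real, true c about 0.71, 150 runs.

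| Model | c in new patients | Calibration slope |
|---|---|---|
| All 33, ordinary logistic (apparent c 0.80) | 0.64 | 0.35 |
| All 33, ridge | 0.67 | 1.2 |
| Seven pre-specified, including all 5 real | 0.69 | 0.83 |

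Screening the 33 at p < 0.05 before ordinary logistic regression gave a slope of about 0.61. With independent predictors and true c 0.72, all 33 entered gave apparent c 0.81, 0.66 in new patients and slope 0.38. Nine candidates gave 0.75, 0.69 and 0.74.

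**6. Single-factor tests.** For 33 null factors each tested at 5%, 33 × 0.05 = 1.65 false positives are expected. If they are independent, the chance of at least one is 1 − 0.95³³ = 82%.

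**The case against.** The strongest reply is that the plan never says it will put 33 variables into one unpenalised model. A reader might infer that it screens at least 33 declared candidates, that the regression is unpenalised, and that it will therefore be badly overfitted. The documents support none of these as stated.

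- The 33 are measurements collected, not a declared list. Footnote 1 describes a biological assessment and does not call its items candidates. INR and PT overlap. Against that, CBC, pharmacokinetics and genomics each count once, and age, sex, tumour type and TKI are left out. The true number is unknown.
- The text is silent on penalisation and on univariable screening. It excludes neither and prescribes neither.
- Severe overfitting is conditional on how the analysis is done. The nine geriatric items alone give shrinkage of 0.76 to 0.87 for R² of 0.15 to 0.30: moderate, although 0.67 at R² of 0.10. A short pre-specified model could reach 0.9 within the present wording.

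Two cautions about the numbers also stand. Seven parameters are supported only at the optimistic R² of 0.30, and the seven-predictor simulation was given all the real predictors, which investigators would not know. In addition, the loss of discrimination relative to ridge is small (0.64 against 0.67). The larger defect is calibration, which matters most if individual risks are issued, and the plan describes no risk score.

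What survives is that the size is unjustified for the primary objective and no safeguard is stated. The four named domains invite a long candidate list, and no shorter one exists in the plan.

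**Conclusion.** The concern holds in conditional form. The 250 patients are justified for the precision of a 30% rate, and nothing shows that they suffice for the primary prediction objective. With about 33 measurements and about 75 events, ordinary logistic regression on all of them, or after p-value screening on the same data, is likely to overfit seriously: coefficients would need multiplying by roughly 0.4 to 0.7 to hold in new patients. The event count follows from the plan's own rate. The shrinkage range rests on the assumed R² and one parameter per measurement, and the simulation on its chosen correlation and number of real predictors.

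This should be settled before outcomes are examined, because it concerns the primary objective and the choice of model cannot credibly be made afterwards.

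**What to change.** **In 'Number of subjects'**, state that 250 is the basis for the rate only, and that about 75 events support roughly 2 to 7 unpenalised parameters, depending on the assumed R².

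**In 'Analysis of toxicity'**, before outcomes are examined (including at the intermediate analysis after 150 inclusions), commit to one of two routes:
1. List all candidates and fit them by ridge or elastic-net logistic regression with a cross-validated penalty. Ridge alone does not select factors, so say how individual factors will be reported.
2. Pre-specify, on clinical grounds, a short list within the parameter budget.

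Under either route, do not select by univariable p-value, report bootstrap optimism-corrected c and calibration slope, and label all other single-factor tests exploratory.

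**Cost:** SAP wording and a little more analysis work, with no extra patients or data. The downside is that fewer factors can be claimed individually.
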